## 1.6 ENDPOINT ANALYSIS

### 1.6.1 PRIMARY ENDPOINT ANALYSIS

For the primary outcome, we will calculate the difference in the AFEQT global questionnaire score (as this is a continuous variable) at baseline and at 6 months and perform a comparison between the patients randomized to the Apple Watch and patients randomized to Withings Move. This will be calculated as per standard AFEQT calculations, which result in a summary score for this continuous outcome (which ranges from 0 to 100). We will use a t-test for this comparison. As this is an RCT, we expect that confounding will be minimal. If patients are missing outcome data, we will use the last observation carried forward for the patient-reported outcomes. Missing covariates will be set to missing.

At 12 months, we will also perform the same analysis, but this will be as an exploratory secondary endpoint. If a patient drops out, we will carry forward the most recent patient-reported outcome measure response.

We will also retrospectively compare AFEQT global questionnaire at months 1, 2, 3, 4, 5.

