## SECTION I: RESEARCH PLAN

### 1. Statement of Purpose:

State the scientific aim(s) of the study, or the hypotheses to be tested.

We plan to conduct a randomized, controlled trial to determine the impact of the Apple Watch Series 6 on both patient-reported outcomes and clinical utilization over 1 year. Our research method will employ a patient-centered health data-sharing platform (called Hugo) for real-world surveillance of outcomes in 150 total patients after they receive direct current cardioversion (DCCV) or catheter ablation for treatment of atrial fibrillation or atrial flutter. We will recruit a total of 150 patients across 3 clinical sites- 60 at Yale-New Haven Hospital, 60 at the Mayo Clinic, and 30 at Duke Health- before they undergo DCCV for atrial fibrillation or atrial flutter or after they undergo catheter ablation for atrial fibrillation or atrial flutter. Half of the patients will be randomized to receive the Apple Watch Series 6, while half will receive a control device (Withings Move). Patients will then be queried about specific symptoms related to atrial fibrillation and medication adherence monthly for a total of 6 times post-procedure (6 months) and also at 12 months. This project will provide novel and needed post-market data about the recently cleared Apple Watch Series 6 ECG and irregular rhythm detection notification features and, on a larger scale, help delineate the impact of an innovative digital health technology on real-world patient outcomes.

**Specific Aim 1:** To assess the impact of using the Apple Watch ECG and irregular rhythm notification features on patient-reported outcomes and clinical utilization after patients receive cardioversion or catheter ablation for atrial fibrillation or atrial flutter.

**Specific Aim 2:** To determine the accuracy of the Apple Watch ECG compared to physician interpretation of 12-lead ECGs obtained in routine clinical care.

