For patients undergoing cardioversion, the RA will attempt to complete all of the enrollment steps before the patient's procedure (cardioversion). Review of and signing of the consent will always be required prior to the procedure. In order to not impact the clinical workflow, some enrollment procedures may be completed post-operatively, if necessary, due to time constraints. If any part of enrollment needs to be completed post-procedure, the RA will always wait a minimum of 20 minutes after the patient is brought into recovery to allow any sedatives to wear off and confirm with the post-op nursing staff that the patient is awake, and that it is acceptable to approach them. Before proceeding with any enrollment procedures, the RA will then confirm the patient is alert and oriented by asking the patient to confirm their name, why they are in the hospital, and what city they are currently in. They will be asked to confirm that they recall the study and are amenable to continuing the enrollment process. The RA will aim to only have items such as syncing the devices to the phone and/or connecting any portal to Hugo, to be completed after the procedure. The baseline survey will be prioritized to be completed, after informed consent, pre-procedure.

For patients who had undergone catheter ablation for atrial fibrillation or atrial flutter, all enrollment procedures will occur only on the first post-procedural day, when the patient is generally recovering and awaiting discharge.

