The RA will record the total time (minutes) for enrollment of each patient, including: device and account setup, in-person consenting, baseline survey (if the RA is present), ECG measurement (if performed) and SpO2 measurement (for Apple Watch patients). The RA will record a total time, and segment the times into discrete enrollment steps, if possible. The RA will not record time that the RA is not with the patient (for example, when the patient is undergoing cardioversion). The RA will also record enrollment type (inpatient or outpatient, with all patients undergoing catheter ablation considered inpatients) within Hugo. After enrollment, patients will also receive a follow-up email that contains their consent form as well as to again provide contact information should they have any questions or concerns about the study.

If a patient refuses to participate, then we will note the number of people who refused. If the patient is agreeable, we will then administer a short questionnaire to understand his/her rationale for not participating in the study, to understand potential reasons for non-participation. Please see Appendix for questionnaire.

If for any reason, portal and/or device connections cannot be completed at the time of enrollment (i.e., there is not enough time to complete, patient does not have their passwords with them, etc.), the RA will follow up with the patient via phone to finish the connections. Up to 3 attempts will be made to contact the patient. If there is no response via phone, the study team will send a letter via postal mail, asking the patient to complete their connections.

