### 1.4 SAMPLING PROCEDURE, SAMPLE SIZE AND POWER CALCULATION

The study sample size was calculated assuming 80% power to detect an effect size of 8.8 on the AFEQT questionnaire (slightly higher than the minimal clinically important difference of 5), with alpha 0.05.

We expect that drop-out rate will be close to zero in this study as patients are followed passively and the burden on patient is minimal. In terms of non-completion of the 6-month AFEQT Questionnaire, our

current study accounts for an estimated drop-out rate of 8% at 6 months based on the use of the AFEQT score from Holmes DN et al Circ Cardiovasc Qual Outcomes 2019, in which the mean  $\pm$  SD was  $79.0 \pm 18.5$  and assuming an effect size of 8.8 on the AFEQT questionnaire, which is higher than the minimal clinically important difference of 5.

If patient drop-out or loss to follow-up occurs, then we will carry forward the last patient-reported outcome measure response. If an electronic health record data connection is lost for a study participant, we will only include the follow-up duration when data were available in the utilization endpoint analyses.

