### 1.6.2 SECONDARY ENDPOINT ANALYSIS

The secondary clinical utilization outcomes will be compared between the two groups. Data obtained through Hugo will be used to obtain most outcomes. As these will intended to be composite outcomes, we will use the t-test or the Wilcoxon rank-sum test for comparison between the Apple Watch and Withings arms.

We will also use the t-test for comparison of the individual domains of the AFEQT questionnaire.

Electronic health records will be used to review ECG tracings. We will also trend patients' monthly responses about anticoagulation adherence. These analyses will be conducted for the entire studied population.

The secondary outcomes for accuracy of Apple Watch Software Features that will be compared are a comparison of the heart rhythm (identical to 12-lead ECG or different), rate (difference in beats per minute), and intervals: PR, QRS, and QT interval (difference in milliseconds) between what is assessed by the Apple Watch ECG feature and 12-lead ECGs during hospitalization or outpatient follow-up. Inter-observer and intra-observer agreement in assessment of the Apple Watch ECGs will be assessed using intraclass correlation coefficient (ICC).

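### The primary AFEQT analysis is an unadjusted t-test on change. It is valid, but adjusting for the baseline score, procedure and site would give more precision at almost no cost.

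*SAP*

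**What the plan says.** SAP 1.6.1 takes each patient's difference between the baseline and 6-month AFEQT global scores and compares the arms: "We will use a t-test for this comparison. As this is an RCT, we expect that confounding will be minimal". The 12-month comparison repeats this analysis as an exploratory endpoint. For the domain scores, SAP 1.6.2 says: "We will also use the t-test for comparison of the individual domains of the AFEQT questionnaire".

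Neither document names a regression model or a covariate for the primary outcome. Even so, SAP 1.6.1 includes the rule "Missing covariates will be set to missing", although the t-test it specifies has no covariates.

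Three design features bear on this:

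- **Sites.** Recruitment is split as "60 at Yale-New Haven Hospital, 60 at the Mayo Clinic, and 30 at Duke Health". The protocol describes central 1:1 randomisation and states no stratification factors.
- **Baseline timing.** For cardioversion patients, "The baseline survey will be prioritized to be completed, after informed consent, pre-procedure". For ablation patients, "all enrollment procedures will occur only on the first post-procedural day".
- **Recorded enrolment type.** This is coded as "inpatient or outpatient, with all patients undergoing catheter ablation considered inpatients", so it does not separate the two procedures.

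**The concern.** A change score uses the baseline in one fixed way: it assumes that each extra point at baseline carries one extra point to 6 months. The correlation between the two scores will normally be below 1. Subtraction then over-corrects and leaves variance that an estimated slope would remove. The SAP's reason for not adjusting deals only with confounding. It does not address precision, or the chance that the arms start at different mean scores.

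The missing-covariate rule adds a separate ambiguity: a reader cannot tell whether an adjusted model was intended.

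A smaller point concerns procedure. Baseline is taken on different sides of the procedure in the two groups, so mean change may differ between cardioversion and ablation patients. Randomisation keeps this from biasing the arm contrast, but it can add variance, and the planned test has no term to absorb it.

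At stake are the width of the primary confidence interval and power that the sample size leaves little room to lose.

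**Working it through.** **Inputs from the SAP.** Difference 8.8 points, SD 18.5 (reported with a mean of 79.0), power 80% and a minimal clinically important difference of 5 (1.4); two-sided 0.05 (1.1). On non-completion, 1.4 says the "current study accounts for an estimated drop-out rate of 8% at 6 months". The total is 150, or 75 per arm.

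**Assumptions.** The documents do not give the baseline-to-6-month correlation (rho), so a range is used. The SD is 18.5 at both times unless stated.

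**The plan's own figure.** The normal formula for 8.8 points and SD 18.5 gives 70 per arm, 140 in all. Allowing for 8%, 140/0.92 = 152.2, so 153, within 3% of 150. In reverse, 75 × 0.92 = 69 per arm gives 79.2% power by noncentral t. The stated sizing reproduces.

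**Residual SDs**

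- Change score: SD_change = √(SDb² + SD6² − 2·rho·SDb·SD6). With equal SDs this is 18.5·√(2(1−rho)).
- ANCOVA on baseline: SD_ANCOVA = SD6·√(1−rho²).
- Difference in variance: (SDb − rho·SD6)², which is never negative. With equal SDs it is SD²(1−rho)², and the ratio ANCOVA/change is (1+rho)/2.

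At rho 0.5, for example, SD_change = 18.5·√1 = 18.5 and SD_ANCOVA = 18.5·√0.75 = 16.0, a 25% saving in variance.

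**Power for 8.8 points, 69 completers per arm (noncentral t)**

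| rho | SD: change / ANCOVA | Power: t-test on change | Power: ANCOVA |
|---|---|---|---|
| 0.3 | 21.9 / 17.7 | 65% | 83% |
| 0.4 | 20.3 / 17.0 | 72% | 86% |
| 0.5 | 18.5 / 16.0 | 79% | 89% |
| 0.6 | 16.6 / 14.8 | 87% | 93% |
| 0.7 | 14.3 / 13.2 | 95% | 97% |
| 0.8 | 11.7 / 11.1 | 99% | nearly 100% |

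**95% CI half-width**, t(0.975)·SD·√(2/69): 7.4 vs 5.9 points at rho 0.3, 6.2 vs 5.4 at 0.5, 4.8 vs 4.4 at 0.7.

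**Unequal SDs** (6-month SD 18.5, rho 0.5). Baseline SD 15: 85% vs 89%. Baseline SD 22: 71% vs 89%.

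**Chance imbalance.** The between-arm difference in mean baseline score has SD 18.5·√(2/69) = 3.15 points. A difference of that size shifts the change-score estimate, relative to the baseline-adjusted one, by (1−rho)·3.15: 2.2, 1.6 or 0.9 points at rho 0.3, 0.5 or 0.7.

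**Procedure, for illustration only.** A gap g in mean change between procedures, with a proportion p having one of them, adds g²·p(1−p) to the variance. The documents give neither g nor p. With g = 10 and p = 0.5 this adds 25, and t-test power at rho 0.5 falls from 79% to 76%. With g = 5 it falls to 78.5%. In a simulation (4,000 runs, rho 0.5, 10-point gap, sites 40/40/20), power was 77% for the t-test, 87% for ANCOVA on baseline, and 89% with procedure and site added.

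**The case against.** The strongest reply is that this is an efficiency choice and not an error. The t-test is valid, the stated sample size reproduces, and no passage contradicts another. That stands, and it is why the point is an improvement and not a correction.

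A second reply is that the SAP carries the last response forward, so about 75 per arm would be analysed instead of 69. That is a fair reading. At 75 per arm, counting carried-forward values as genuine 6-month values, power is 69% vs 86% at rho 0.3, 82% vs 92% at 0.5 and 96% vs 98% at 0.7. The planned test then exceeds 80% at rho 0.5, but the gap between methods is much the same. Where only a baseline score exists to carry forward, change is zero by construction. This raises the analysed correlation and slightly reduces ANCOVA's advantage.

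Third, the low power at rho 0.3 is partly a sizing matter. The SD of 18.5 describes a single score and, with equal SDs, equals the SD of change only at rho 0.5. This is correct: the shortfall below 80% should not be put down wholly to the choice of test. ANCOVA would offset it.

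Fourth, rho is unknown, and the gain from procedure and site cannot be computed from the documents. Both are true. Baseline adjustment carries the argument; procedure and site are a low-cost addition.

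**Conclusion.** The concern holds as a matter of precision, not validity. The planned test is unbiased under randomisation, but baseline enters only by subtraction, and procedure and site do not enter at all. For baseline adjustment the direction of the gain is certain: with equal SDs, ANCOVA has the smaller variance at every rho below 1. Its size rests on a correlation the documents do not supply. On the stated assumptions the gain is 10 percentage points of power or more at rho 0.5 and below, and small at 0.7 and above. At rho below 0.5 the t-test falls under 80% power with 69 per arm, while ANCOVA stays above 80% down to rho 0.3, the lowest value shown. The procedure effect is secondary and purely illustrative. The missing-covariate sentence needs resolving in any case. The change should be made, but the trial does not fail without it.

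**What to change.** Before the analysis, amend the SAP as follows:

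1. **Primary analysis (1.6.1).** ANCOVA of the 6-month AFEQT global score on arm, baseline AFEQT global score, procedure (cardioversion or ablation) and site. Report the adjusted mean difference with its 95% CI. Keep the t-test on change as a supportive analysis.
2. **Domains (1.6.2) and 12 months (1.6.1).** Use the same model with the matching baseline score.
3. **Procedure variable.** Define it from the eligibility criterion the patient met. The recorded enrolment type will not serve, because it groups ablation with inpatient cardioversion.
4. **Missing-covariate sentence (1.6.1).** Name the covariates it refers to, or delete it.

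The cost is SAP wording and one derived variable. Baseline AFEQT and site are already collected, and procedure is known from the eligibility checklist. The added terms use 4 degrees of freedom (baseline 1, procedure 1, site 2), with negligible effect on power at this sample size.

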### 1.6.2 SECONDARY ENDPOINT ANALYSIS

The secondary clinical utilization outcomes will be compared between the two groups. Data obtained through Hugo will be used to obtain most outcomes. As these will intended to be composite outcomes, we will use the t-test or the Wilcoxon rank-sum test for comparison between the Apple Watch and Withings arms.

We will also use the t-test for comparison of the individual domains of the AFEQT questionnaire.

Electronic health records will be used to review ECG tracings. We will also trend patients' monthly responses about anticoagulation adherence. These analyses will be conducted for the entire studied population.

The secondary outcomes for accuracy of Apple Watch Software Features that will be compared are a comparison of the heart rhythm (identical to 12-lead ECG or different), rate (difference in beats per minute), and intervals: PR, QRS, and QT interval (difference in milliseconds) between what is assessed by the Apple Watch ECG feature and 12-lead ECGs during hospitalization or outpatient follow-up. Inter-observer and intra-observer agreement in assessment of the Apple Watch ECGs will be assessed using intraclass correlation coefficient (ICC).

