### **Secondary Clinical Outcomes**

1. Change within individual domains of AFEQT questionnaire (symptoms, daily activities, treatment concern, and treatment satisfaction) monthly (at 1, 2, 3, 4, 5, and 6 months as well as at 12 months)
2. Additional clinical treatment for atrial fibrillation or flutter at 6 and 12 months: a composite outcome of rhythm control intervention, which is defined as at least one additional cardioversion, initiation of antiarrhythmic medical therapy, dose escalation of antiarrhythmic medication, change to another antiarrhythmic medication, or ablation for atrial fibrillation or flutter. The medication data will be obtained primarily from electronic health record data.
3. Acute care use at 6 and 12 months: emergency department visits, observation stays, all hospitalizations
4. Outpatient care use at 6 and 12 months: outpatient primary care visits, outpatient cardiology or cardiac electrophysiology visits, and scheduled telephone encounters.
5. Rhythm-related diagnostic testing at 6 and 12 months: total ECGs and total outpatient heart rhythm monitors
6. Anticoagulation persistence: through adopting the Brief Medication Questionnaire and asking patients if they have taken their anticoagulant, and for how many days in the past 1 week (monthly at 1, 2, 3, 4, 5, and 6 months as well as at 12 months)

For the primary outcome, we will calculate the difference in the AFEQT global questionnaire score at baseline and 6 months and perform a comparison between the patients randomized to the Apple Watch and patients randomized to Withings Move.

The secondary clinical utilization outcomes will be compared between the two groups. Data obtained through Hugo will be used to obtain most outcomes. Electronic health records will be used to review ECG tracings. We will also trend patients' monthly responses about anticoagulation adherence.

The secondary outcomes for accuracy of Apple Watch Software Features that will be compared are a comparison of the heart rhythm (identical to 12-lead ECG or different), rate (difference in beats per minute), and intervals: PR, QRS, and QT interval (difference in milliseconds) between what is assessed by the Apple Watch ECG feature and 12-lead ECGs during hospitalization or outpatient follow-up. This will be a blinded independent assessment of the Apple Watch ECG, and we will calculate both inter-observer reliability (among two reading cardiologists of Apple Watch ECGs), as well as intra-observer reliability.

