Participants will undergo the possible inconvenience of filling out electronic patient-reported outcome measure surveys, which should take no more than 10 minutes monthly for a total of 8 times, as well as a close-out questionnaire that should take no longer than 5 minutes. Participants will also experience the possible inconvenience of wearing an Apple Watch or Withings Move for extended periods of time and syncing these devices with the Hugo Health platform.

Although the Apple Watch ECG and irregular rhythm notification detection features have been cleared by the FDA as a de novo classification device, the FDA's approval letter noted multiple identified risks to health, which were:

Poor quality ECG signal resulting in failure to detect arrhythmia; misinterpretation and/or over-reliance on the device output, leading to: failure to seek treatment despite acute symptoms and/or discontinuing or modifying treatment for chronic heart conditions; false-negative resulting in failure to identify arrhythmia and delay of further evaluation or treatment; and false-positive resulting in additional unnecessary medical procedures. Further, we will clearly state to the patients that this study should in no way impact their regular care plans.

**10. Minimizing Risks:** Describe the manner in which the above-mentioned risks will be minimized.

All patient data will be collected, handled, and stored according to the most rigorous accepted standards. Staff involved in the study will be appropriately trained to maximize data security and technical systems will meet or exceed requirements imposed by HIPAA. Sensitive information will always be encrypted in transit and at rest.

11. **Data and Safety Monitoring Plan:** Include an appropriate Data and Safety Monitoring Plan (DSMP) based on the investigator's risk assessment stated below. (Note: the HIC will make the final determination of the risk to subjects.)

- a. What is the investigator's assessment of the overall risk level for subjects participating in this study? Minimal risk to patients
- b. If children are involved, what is the investigator's assessment of the overall risk level for the children participating in this study? No children will be involved in this study
- c. Include an appropriate Data and Safety Monitoring Plan. Examples of DSMPs are available here <http://your.yale.edu/policies-procedures/forms/420-fr-01-data-and-safety-monitoring-plans-templates> for
  - i. Minimal risk

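### Anticoagulation persistence is a listed secondary outcome, but its only planned analysis is a trend, with no comparison between the randomised arms

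*SAP*

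**What the plan says.** The protocol's list of Secondary Clinical Outcomes has as item 6 "Anticoagulation persistence: through adopting the Brief Medication Questionnaire and asking patients if they have taken their anticoagulant". The item also covers the number of days taken over the preceding week, at each of months 1 to 6 and at month 12. It is therefore a self-reported item with seven scheduled assessments.

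The analysis is described in four places: the protocol text after that list, protocol item 12 (Statistical Considerations), SAP 1.1 and SAP 1.6.2. The wording is in effect the same in each: "We will also trend patients' monthly responses about anticoagulation adherence". SAP 1.6.2 then adds "These analyses will be conducted for the entire studied population", a sentence that appears nowhere else in either document.

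Other secondary outcomes are treated differently. SAP 1.6.2 says "The secondary clinical utilization outcomes will be compared between the two groups" and that "we will use the t-test or the Wilcoxon rank-sum test for comparison between the Apple Watch and Withings arms". It also names a t-test for the AFEQT domains.

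**The concern.** Aim 1 of the protocol is the impact of the watch on patient-reported outcomes and clinical utilization. Randomisation lets a difference between arms be attributed to the watch; a time course alone does not. For item 6 the plan describes only a time course.

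This outcome has some safety interest. Protocol item 9 (Risks) repeats the regulator's concern that over-reliance on the device could lead to "discontinuing or modifying treatment for chronic heart conditions". The Follow-Up section says patients get no guidance on how to respond to a rhythm notification, because the study wants to observe what they do. Anticoagulant use is one behaviour that could change. If the comparison is not specified in advance, any later one is post hoc, with the measure, time point and denominator chosen after the data are in hand.

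**Working it through.** **1. The plan's own figure.** The documents give no sample size, rate or effect for anticoagulation. The only calculation is for AFEQT (SAP 1.4: difference 8.8, SD 18.5, 80% power, alpha 0.05, 8% drop-out).

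- Per arm: 2 × (1.96 + 0.84)² × 18.5² / 8.8² = 2 × 7.85 × 342.25 / 77.44 = 69.4, so 70, or 140 in total.
- With drop-out: 140 / 0.92 = 152.2, so 153 (or 140 × 1.08 = 151.2, so 152), against 150 stated.
- Expected at 6 months: 150 × 0.92 = 138, or 69 per arm.

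The stated size reproduces to within 3. It has no bearing on item 6 beyond fixing how many patients are available.

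**2. The planned analyses side by side.**

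| Outcome | Contrast between arms | Method |
|---|---|---|
| Utilization outcomes | Stated | t-test or Wilcoxon rank-sum (SAP 1.6.2) |
| AFEQT domains | Implied by the test | t-test (SAP 1.6.2) |
| Anticoagulation persistence | None stated | Monthly responses trended; no test, model, summary measure or denominator |

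Protocol item 12 also says all outcomes will be examined at 12 months. That adds a time point for item 6 but no method.

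**3. Two readings of the SAP 1.6.2 sentence.**

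- Arms combined: the result is one pooled time course and no contrast.
- All randomised patients, in line with the intention-to-treat statement in SAP 1.1: the analysis set is defined, but the analysis is still a trend and no contrast is named.

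The gap is the same under both.

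**4. What a comparison could show.** The documents give no persistence rate, so the control rate p₁ is assumed to be 70, 80 or 90%, with a lower rate p₂ in the watch arm. The calculation is for a single time point, two-sided alpha 0.05 and a normal approximation. With d = p₁ − p₂ and p̄ their mean, power = Φ{[d − 1.96√(2p̄(1−p̄)/n)] / √([p₁(1−p₁) + p₂(1−p₂)]/n)}.

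Solving for d at 80% power, in percentage points:

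| n per arm | p₁ = 70% | p₁ = 80% | p₁ = 90% |
|---|---|---|---|
| 75 | 22.4 | 20.9 | 17.8 |
| 69 | 23.4 | 21.9 | 18.7 |
| 52 | 27.0 | 25.5 | 22.2 |
| 45 | 29.0 | 27.6 | 24.2 |

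The last two rows assume that about 75% or 65% of the 69 take an anticoagulant (52/69 and 45/69). At 69 per arm, power for a 10-point difference is 23, 27 and 38%.

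The 95% CI half-width when both arms have rate p is 1.96 × √(2p(1−p)/n):

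- n = 69: 15.3, 13.3 and 10.0 points for p = 70, 80 and 90%. For example, 1.96 × √(0.32/69) = 0.133.
- n = 45: 18.9, 16.5 and 12.4 points.

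An arm contrast can be estimated, but only coarsely.

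**The case against.** The strongest reply has four parts.

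*The phrase about the whole population may not mean pooling.* This stands. A reader might infer that the plan merges the arms and so hides any watch effect. The documents do not establish that. The sentence is in SAP 1.6.2 only, its referent is unclear (it follows both the ECG review and the trend sentence), and intention-to-treat gives it a natural alternative meaning. A trend could also be shown by arm. The point made here does not need the pooled reading.

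*The general promise to compare secondary utilization outcomes covers it.* This does not stand. Self-reported days of medication in the past week is not utilization, and the SAP puts "monthly responses about anticoagulation adherence" in a sentence separate from the between-group one.

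*The denominator and missing-data rules are unspecified, not wrong.* This stands. A reader might infer that patients who never took an anticoagulant count as non-persistent, or that those who stop answering are carried forward as persistent. Neither is stated. The question refers to the patient's own anticoagulant, which presupposes one. Carry-forward is general in SAP 1.4, tied to missing primary outcome data in 1.5, and placed under the primary endpoint in 1.6.1. Whether it reaches this item is unclear.

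*The trial is too small for the comparison to matter.* This stands in part. It rules out a powered test, but not reporting an estimate with its interval.

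**Conclusion.** The concern holds in this form: for a listed secondary outcome of a randomised trial, no between-arm contrast is prespecified under either reading of SAP 1.6.2, so the plan as written does not estimate the watch's effect on anticoagulant use. That conclusion rests on the text alone and needs no assumed figure.

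The consequence is moderate. The primary endpoint is untouched, and because the arm of each patient is known, a comparison remains possible later, though only post hoc. It would be wrong to say that the trial cannot examine the question, or that a planned comparison would reliably detect harm. Under the assumed control rates, only differences of roughly 18 to 23 points with 69 to 75 per arm, or 22 to 29 points with 45 to 52 users per arm, reach 80% power.

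The link to the over-reliance risk is an inference. The risk text speaks of treatment for chronic heart conditions and does not name anticoagulants, and the item records whether the drug was taken, not why it was stopped.

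**What to change.** In SAP 1.6.2, replace the trend-only sentence for this outcome with a prespecified comparison by randomised arm:

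- **Measure:** days taken in the past 7, or the proportion taking it on all 7 days, chosen in advance.
- **Time points:** 6 and 12 months, for example from a repeated-measures model using months 1 to 6 and 12 with arm, month and their interaction.
- **Denominator:** patients with an anticoagulant on the baseline medication list. The baseline variables in the Analytic Plan and SAP 1.2 do not include anticoagulant use, so this must come from the EHR medication lists collected through Hugo (protocol Section IV, item 1). Using the list as it stood at randomisation keeps the comparison a randomised one within users.
- **Reporting:** the arm difference with a 95% confidence interval, labelled as an estimate and not a powered test.
- **Missing data:** state that carry-forward does not apply to this item.
- **Wording:** say whether the whole-population sentence means all randomised patients.

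If the sponsor wants description only, the minimum is to relabel item 6 as descriptive and present it by arm.

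The cost is SAP wording, one extra model, a step to extract baseline users from the EHR data, a smaller denominator and a wide interval. No new data collection is needed, provided the medication lists are available at baseline.
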